5. CONTRAINDICATIONS / WARNINGS AND PRECAUTIONS

5.1 Contraindications

Cingal has the following contraindications per its approved labeling (IFU AML 500-277):

5.1.1 CINGAL CONTRAINDICATIONS:

Cingal is composed of cross-linked hyaluronic acid, triamcinolone hexacetonide and inactive ingredients. The following pre-existing conditions may constitute relative or absolute contraindications to the use of Cingal:

- Hypersensitivity to the active substance or to any of the excipients contained in Cingal
- Pre-existing infections of the skin region of the intended injection site
- Known infection of the index joint
- Known systemic bleeding disorders
- Weak populations including children and pregnant or lactating women

The ancillary medicinal substance, triamcinolone hexacetonide, is contraindicated in the case of:

- active tuberculosis

- herpes simplex keratitis
- acute psychoses
- systemic mycoses and parasitoses (strongyloid infections)

5.1.2 CINGAL INVESTIGATIONAL USE CONTRAINDICATIONS:

The same contraindications in the approved Cingal labeling apply to investigational use in the hip, shoulder or ankle.

5.2 WARNINGS / PRECAUTIONS:

5.2.1 CINGAL WARNINGS

Cingal has the following Warnings and Precautions per its approved labeling:

PRECAUTIONS

General:

- Those precautions normally considered during injection of substances into joints are recommended.
- Appropriate examination of any joint fluid present is necessary to exclude a septic process.
- Only medical professionals trained in accepted injection techniques for delivering agents to joint spaces should inject Cingal for this application.
- The synovial space should not be overfilled.
- If pain increases during the injection procedure, the injection should be stopped and the needle withdrawn.
- A marked increase in pain accompanied by local swelling, further restriction of joint motion, fever, and malaise are suggestive of septic arthritis. If this complication occurs and the diagnosis of sepsis is confirmed, appropriate antimicrobial therapy should be instituted.
- Single Use only; reuse of the contents of the syringe may result in infection and increase occurrence of adverse events.

Triamcinolone hexacetonide

- This product contains a corticosteroid and so should be used with caution in patients suffering from the following conditions:
 - cardiac insufficiency, acute coronary artery disease,
 - hypertension,
 - thrombophlebitis, thromboembolism
 - myasthenia gravis,

- osteoporosis,
- gastric ulcer, diverticulitis, ulcerative colitis, recent intestinal anastomosis,
- exanthematous diseases,
- psychosis,
- Cushing's syndrome,
- diabetes mellitus,
- hypothyroidism,
- renal insufficiency, acute glomerulonephritis, chronic nephritis,
- cirrhosis,
- infections that cannot be treated with antibiotics,
- metastatic carcinoma.

- All corticosteroids may increase calcium excretion.
- The product must not be administered intravenously, intraocularly, epidurally or intrathecally.
- Intra-articular injection should not be carried out in the presence of active infection in or near joints.
- The load on strained joints in particular should be lightened immediately after the injection to avoid overloading.
- If, during treatment, the patient develops serious reactions or acute infections, the treatment must be stopped and appropriate treatment given.
- Caution should be used in the event of exposure to chickenpox, measles or other communicable diseases, since the course of specific viral diseases such as chickenpox and measles may be particularly severe in patients treated with glucocorticoids. At particular risk are individuals with no history of chickenpox or measles infection. If such individuals should come into contact with chickenpox or measles sufferers during treatment with Triamcinolone hexacetonide, prophylactic treatment should be considered as appropriate.
- Menstrual irregularities may occur and in postmenopausal women vaginal bleeding has been observed. This possibility should be mentioned to female patients but should not deter appropriate investigations as indicated.
- Triamcinolone hexacetonide contains sorbitol. Patients with very rare hereditary problems of fructose intolerance should not take this medicine.
- Glucocorticoids may induce growth suppression in children. The Safety of Cingal® in pediatric populations has not been established.

Interaction with other medicinal products

- Amphotericin B injection and potassium-depleting agents: Patients should be monitored for additive hypokalaemia.

- Anticholinesterases: The effect of anticholinesterase agent may be antagonised.
- Anticholinergics (e.g. atropine): Additional increase of intraocular pressure is possible.
- Anticoagulants, oral: Corticosteroids may potentiate or decrease anticoagulant effect. For this reason, patients receiving oral anticoagulants and corticosteroids should be closely monitored.
- Antidiabetics (e.g. sulfonylurea derivatives) and insulin: Corticosteroids may increase the levels of glucose in the blood. Diabetic patients should be monitored, especially on instigation and discontinuation of treatment of corticosteroids and if the dosage is changed.
- Antihypertensives, including diuretics: The reduction in arterial blood pressure may be diminished.
- Antituberculosis drugs: Isoniazid serum concentrations may be decreased.
- Cyclosporin: When used concomitantly, this substance may produce an increase in both cyclosporin and corticosteroid activity.
- Digitalis glycosides: Concomitant administration may increase the likelihood of digitalis toxicity.
- Hepatic Enzyme Inducers (e.g. barbiturates, phenytoin, carbamazepine, rifampicin, primidone, aminoglutethimide): There may be increased metabolic clearance of Triamcinolone hexacetonide. Patients should be carefully observed for possible reduced effect of Triamcinolone hexacetonide, and the dosage should be adjusted accordingly.
- Human growth hormone (somatropin): The growth-promoting effect may be inhibited during long-term therapy with Triamcinolone hexacetonide.
- Ketoconazole: Corticosteroid clearance may be decreased, resulting in increased effects.
- Non-depolarising muscle relaxants: Corticosteroids may decrease or enhance the neuromuscular blocking action.
- Non-steroidal anti-inflammatory agents (NSAIDs): Corticosteroids may increase the incidence and/or severity of gastrointestinal bleeding and ulceration associated with NSAIDs. Corticosteroids may also reduce serum salicylate levels and therefore decrease their efficacy. Conversely, discontinuing corticosteroids during high-dose salicylate therapy may result in salicylate toxicity. Caution must be exercised during concomitant use of acetylsalicylic acid and corticosteroids in patients with hypoprothrombinaemia.
- Oestrogens, including oral contraceptives: Corticosteroid half-life and concentration may be increased and clearance decreased.
- Thyroid drugs: Metabolic clearance of adrenocorticoids is decreased in hypothyroid patients and increased in hyperthyroid patients. Changes in thyroid status of the patient may necessitate adjustments to the dosage of adrenocorticoids.
- Vaccines: Neurological complications and a diminished antibody response may occur when patients taking corticosteroids are vaccinated. (see section 4.3)
- Medicines that prolong the QT interval or induce torsade de pointes:

- Concomitant treatment with triamcinolone hexacetonide and class Ia antiarrhythmic agents such as disopyramide, quinidine and procainamide, or other class II antiarrhythmic drugs such as amiodarone, bepridil and sotalol, is not recommended.
- Extreme caution is required in cases of concomitant administration with phenothiazines, tricyclic antidepressants, terfenadine and astemizole, vincamine, erythromycin i.v., halofantrine, pentamidine and sultopride.
- Combination with agents that cause electrolyte disturbances such as hypokalaemia (potassium-depleting diuretics, amphotericin B i.v. and certain laxatives), hypomagnesaemia and severe hypocalcaemia is not recommended.
- Interactions with laboratory tests - Corticosteroids may interfere with the nitroblue tetrazolium test for bacterial infection, producing false-negative results.
- Athletes should be informed that this medicinal product contains an ingredient (e.g. triamcinolone hexacetonide) that may produce a positive result in anti-doping tests.

Fertility, Pregnancy and Lactation

- The safety of Cingal in pregnant and lactating women has not been established.
- Fertility, pregnancy and lactation: Triamcinolone crosses the placenta. Corticosteroids are teratogenic in animal experiments. The significance of this fact for humans is not exactly known, but so far the use of corticosteroids has not been shown to increase the incidence of malformations. The product should be used during pregnancy only if the benefit to the mother is clearly greater than the risk to the fetus. Triamcinolone hexacetonide is excreted in human milk, but is not likely to have any effect on the child at therapeutic doses. Corticosteroid therapy may cause menstrual disorders and amenorrhea.

5.2.2 CINGAL INVESTIGATIONAL USE WARNINGS AND PRECAUTIONS:

The same warnings/precautions in the approved Cingal labeling apply to investigational use in the hip, shoulder or ankle.

5.3 Usage in Pregnancy

The safety of Cingal in pediatric populations, pregnant and lactating women has not been established.

6. ENDPOINTS

6.1 Primary Endpoint:

- Reduction of index hip Numerical Rating Scale (NRS) pain on walking from baseline to 6 Months post injection.

6.2 Secondary Endpoints:

- Improvement in Lequesne Hip index hip from baseline to 6 months post injection.
- Improvement in Patient Global Assessment (PGA) from baseline to 6 months post injection.
- OMERACT-OARSI responder rate in the index hip at 6 months post injection.
- Time to treatment failure
- Reduction in Medication usage from baseline to 6 months post injection.

6.3 Exploratory Endpoints

Any comparisons across timepoints (baseline to 6 months) not described in the primary or secondary endpoints, including but not limited to:

- Demographics
- Medical History
- History of joint osteoarthritis
- Rescue Medication Use
- Treatment Failure
- Injection procedure
- Concomitant medications
- Non-drug therapy

6.4 Safety Endpoint:

The incidence, severity, and relationship to treatment of all Adverse Events (AE) will be collected from the treatment injection to the 6 month assessment.

6.5 Trial Design

This is a prospective, expanded indications multi-center, open-label study to evaluate safety and performance of injections of Cingal for relief of pain in patients with a diagnosis of an osteoarthritic hip joint.

The subjects in this study will be patients with a diagnosis of osteoarthritic (OA) joint who the investigator determines are appropriate candidates for treatment with a viscoelastic injection of Cingal.

Up to 25 subjects will be enrolled and treated at up to 10 investigational sites in the EU. Subject participation will last approximately 6 Months, with visits scheduled at Screening, Baseline, 1 month,

3 month and 6 months.

6.6 Enrollment Criteria

At screening visit:

6.6.1 Screening Inclusion Criteria

1. Age 18 years or older
2. Body Mass Index (BMI) $\leq 35 \text{ kg/m}^2$
3. Diagnosis of symptomatic osteoarthritic joint in the index hip (Kellgren-Lawrence grade I to III) to be treated with CINGAL injection.
4. Failed conservative treatment for joint osteoarthritis.
5. NRS on walking ≥ 4 and ≤ 9 in index hip.
6. Subject must be willing to abstain from other treatments of the index hip for the duration of the study.
7. Subject is willing to discontinue all analgesics including NSAIDs, except acetaminophen/paracetamol, at least seven days before the treatment injection and through the completion of the study.
8. Subject is willing to use only acetaminophen/paracetamol (up to a maximum of 4.0 grams per day per the package insert) for the treatment of joint pain for the duration of the study. At least forty-eight hours prior to the Baseline Visit and each follow-up assessment, the subject is willing to discontinue use of acetaminophen/paracetamol.
9. Subject is willing to maintain a stable dose of oral glucosamine and/or chondroitin sulfate products throughout the study, if taken prior to signing the informed consent form (ICF).
10. Able and willing to provide signed informed consent.

6.6.2 Screening Exclusion Criteria

1. History of hypersensitivity to any of the ingredients in the hyaluronan or corticosteroids
2. Infection or skin disease in the area of the injection site or hip joint
3. NRS pain on walking > 3 the contralateral hip.
4. NRS pain on walking > 3 in the ipsilateral knee or ankle joints.
5. Subject received an injection of Hyaluronic Acid (HA) and/or steroid in either joint within 6 months of signing the informed consent form (ICF). A subject will be excluded if they are planning to receive an HA or steroid injection (other than the study injection) in either joint during the course of this study.
6. Known inflammatory or autoimmune disorders (including rheumatoid arthritis, gout), or other pre-existing medical conditions that, in the opinion of the investigator, could impact treatment of the hip joint or affect the ability of the subject to accurately complete the study questionnaires and comply with the study requirements.
7. Subject is taking medications at the time of signing the ICF which could interfere with the treatment procedure, healing and/or assessments. This includes but is not limited to oral or injectable anticoagulant treatments, anti-aggregant platelet treatment, chronic opioid analgesics. Low dose aspirin used for cardiovascular protection is allowed if a stable regimen is maintained for the duration of the study.
8. Subjects who had an oral, intramuscular, intravenous, rectal suppository or topical (excluded in index hip only) corticosteroid within 30 days of signing the ICF are excluded. Topical corticosteroid use at any site other than the index hip is allowed.
9. Significant trauma to the index hip within 26 weeks of screening
10. Chronic use of narcotics or cannabis.

11. Ligament instability or tear in index hip.
12. Diagnosis of fibromyalgia
13. Diagnosis of osteonecrosis in index hip
14. Subject has significant varus or valgus deformity greater than 10 degrees in either knee.
15. Subject requires consistent use of an assistive device (e.g. wheelchair, walker, etc.)
Occasional use of a cane is acceptable.
16. Uncontrolled diabetes with HbA1c of >7%.
17. Subject is a woman who is pregnant or breastfeeding at the Screening Visit or a woman of child bearing potential who refuses to use effective contraception during the course of the study.
18. Subject is receiving or in litigation for worker's compensation.
19. Otherwise determined by the investigator to be medically unsuitable for participation in this study.

At baseline visit:**6.6.3 Baseline Inclusion Criteria**

1. NRS pain on walking ≥ 4 and ≤ 9 in index hip

6.6.4 Baseline Exclusion Criteria

2. Subject has a decrease of ≥ 2 in the NRS pain on walking from Screening to Baseline in the index hip.
3. Subject has a contraindication to continue with the study treatment injection based on the visual appearance of the synovial fluid aspirate.

7. STUDY PROCEDURES

7.1 Schedule of Events

Assessments	Screening Visit Day -14 to -7 ±2 days	Baseline Visit Day 0	Month 1 Visit	Month 3 Visit	Month 6 Visit
			±3 days	± 7 days	± 7 days
Informed Consent	X				
Evaluation of Enrollment Criteria	X	X			
Demographics	X				
Vital Signs	X				
History Joint OA (Index & Contralateral for hip, knee and ankle)	X				
Medical History	X				
Concomitant Medication	X	X	X	X	X
Assess non-drug therapies	X	X	X	X	X
Adverse Event Assessment		X	X	X	X
Collect & Review Subject Diary		X	X	X	X
Rescue Medication usage / washout		X	X	X	X
Patient Global Assessment (PGA)	X	X	X	X	X
Lequesne index for index and contralateral hip	X	X	X	X	X
Index and Contralateral Joints Pain on Walking (0-10 Numeric Rating Scale) for Hip, Knee and Ankle joint	X	X	X	X	X
Physical Evaluation of Index and Contralateral for Hip, Knee and Ankle joints	X	X	X	X	X
Study Injection		X			
Dispense Subject Diary	X	X	X	X	

7.2 Procedure Description

7.3 Screening Visit (Day -14 to -2 days)

The following screening and eligibility data will be collected.

7.3.1 Informed Consent Form

The subject must sign the Informed Consent Form (ICF) prior to enrollment or undergoing study treatment.

7.3.2 Inclusion / Exclusion Criteria

Confirm subject eligibility against the inclusion and exclusion criteria.

7.3.3 Demographics

The following demographic information will be collected at the Screening Visit:

- Age
- Gender
- Race
- Height
- Weight
- Index hip – left / right
- Index / Contralateral Joint OA Grades for Hip, Knee and Ankle

7.3.4 Vital Signs

Patient will have vital signs assessed.

- Blood pressure
- Pulse
- Temperature

7.3.5 History of Joint Osteoarthritis

Subject's history of osteoarthritis including prior treatments for both index and contralateral hip, knee and ankle joints.

7.3.6 Medical History

The relevant medical history of the index and contralateral hip, knee and ankle joints will include, but is not limited to, an assessment of:

- History of trauma in the joints
- History of surgery in the joints
- History of injections to treat pain in the joints
- History of other treatments in the joints including failed prior treatments including but not limited to corticosteroid injection, HA injection, acupuncture, RICE (Rest, Ice, Compression, Elevation), NSAIDS.

7.3.7 Pain Assessment

Patient reported Pain on walking of the index and contralateral hip, knee and ankle joints will be measured with a Numerical Rating Scale (NRS).

7.3.8 Physical Evaluation of Index & Contralateral Joints

The Investigator will perform the physical evaluation of the index and contralateral hip, knee and ankle joints at the time points included in Schedule of Events, and will include the following assessments:

- Appearance of redness or swelling
- Assessment of pain upon palpation of the joints
- Assessment of comorbidities at the joints

7.3.9 Medications

Medications that the subject may have been taking prior to study enrollment for conditions unrelated to the treatment of osteoarthritis, other than analgesics including NSAIDs, may be continued as long as they will not interfere with study assessments. Low dose aspirin (81 mg) used for cardiovascular protection is allowed if a stable regimen is maintained for the duration of the study.

7.3.9.1 Restricted Medications

All analgesics other than acetaminophen/paracetamol are prohibited during the study. This includes, but is not restricted to, NSAIDs, opioids and topical agents for treatment of osteoarthritis of hip joint. Topical corticosteroids are allowed at any other site other than the hip joint. The analgesic medication use will be monitored at each subject assessment through review of the subject diary.

7.3.9.2 Rescue Medications

Acetaminophen/paracetamol (up to a maximum of 4.0 grams per day per the package insert or as per regional limitations) will be allowed as the rescue medication for the treatment of Osteoarthritis in the index hip for the duration of the study. At least forty-eight hours prior to the Baseline Visit, 1, 3 and 6 Month Assessments the subject should discontinue use of the rescue medication.

The subject should be instructed to track pill usage daily to convey accurate pill counts at follow-up assessments.

7.3.9.3 Concomitant Medications

A medication is considered concomitant if taken after signing the ICF and up to and including the last follow-up assessment. Data on medications will include: medication name, dose, unit, route, frequency, start date, stop date, indication and whether the medication was taken for an AE.

At each study assessment, the subject will be asked about any new medications that were started since the last assessment. Indications for any new medications started after the study treatment will be recorded as AEs, unless the medications are administered for a pre-existing condition.

7.3.9.4 Non-Drug Therapies

Non-drug therapies are any therapies used to treat the hip joint that are not a pharmaceutical treatments.

7.3.9.5 Joint Function Assessment

Subjects will receive assessment of the respective joints for functional use.

7.3.9.6 Subject Diary

Subjects will receive diary for to record rescue medications and concomitant medications.

7.4 Baseline Visit: Treatment Visit (Day 0)

The Baseline Visit (Day 0) will occur 7 to 14 days after the Screening Visit to allow for rescue medication washout. The injection will occur at this Baseline visit along with the following activities:

Before Treatment Injection

- Concomitant Medications
- Current non-drug therapies
- Confirm Medication Washout
 - If subject did not complete medications washout, reschedule the visit to allow washout to be completed.
- Patient Global Assessment (PGA)
- Lequesne Hip index
- Index & Contralateral Hip, Knee and Ankle Joint Pain on Walking (NRS Scale)
 - Confirm Baseline Inclusion & Exclusion Criteria for NRS pain on walking
- Physical Exam of Index and Contralateral Hip, Knee and Ankle Joints

Treatment Procedure

The Treating Physician may perform the Study Injection to the index hip as standard of care dictates or delegate the injection to qualified study staff.

Intra-articular injection of the index hip joint may be conducted under fluoroscopic or ultrasound guidance as required by standard of care treatment. Guidelines for the injection procedural steps are provided below. Modifications to this technique should be recorded in the CRFs.

- Patient is supine, index hip rotated internally 15-20 deg.
- Prep the skin at injection site with 1% betadine solution or equivalent.
- Peri- articular injection site anesthesia by injection of lidocaine or topical refrigerant anesthetic (e.g. ethyl chloride).
- Fluoroscopic or ultrasound guidance may be utilized if required to insert 18-21 gauge needle anteriorly towards the anterior-inferior joint capsule, approximately 8-10 cm below the inguinal ligament and just below the femoral head, taking care to avoid the femoral artery.
- If using fluoroscopic guidance, a small amount of fluoroscopic contrast agent (0.5 to 1.0 ml) should be injected through the needle to verify intra-articular placement.
- If using ultrasound guidance, a small volume of air (up to 0.5 ml) may be injected to verify IA positioning.
- If pooling of the contrast agent or air around the needle tip is observed, the needle should be repositioned.

- When contrast agent or air is successfully injected into the joint, intra-articular placement is confirmed.
- Following confirmation of intra-articular needle placement, the joint may be aspirated to remove synovial fluid.
 - Confirm the Baseline Exclusion for synovial aspirate.
- 4 ml of CINGAL is injected into the joint.
- Intra-articular anesthetic should NOT be administered as part of the injection procedure.
- Following the injection, the patient should be advised to maintain a low level of physical activity for the next 48 hours. Cold therapy and/or acetaminophen/ paracetamol may be prescribed to address short term injection site pain.

Post-Treatment Assessments and Instructions

Prior to leaving the clinic, the subject should be evaluated for local and non-local AEs. All post-treatment signs and symptoms that are unexpected should be recorded as AEs. The expected appearance of the index hip should be discussed with the subject with a request that all unexpected symptoms be reported to a member of the study team.

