4.2 Risks

Any intra-articular injection poses potential risks. However, subjects should incur no additional risks compared to injections of other frequently injected products, such as corticosteroids or diagnostic contrast agents.

Effects associated with Hyaluronic Acid

Hyaluronic acid is a naturally occurring component of the tissues of the body. Cingal is thoroughly tested to determine that each batch conforms to the product quality attributes. Mild to moderate episodes of transient swelling and discomfort have occasionally been observed following intra-articular injection of hyaluronic acid preparations. A risk of infection is possible with the procedure of injecting substances into joints.

Effects associated with Triamcinolone Hexacetonide

For assessment of adverse reactions (ADRs) following terms regarding frequency are used:

very common ($\geq 1/10$)

common ($\geq 1/100$ to $< 1/10$)

uncommon ($\geq 1/1,000$ to $< 1/100$)

rare ($\geq 1/10,000$ to $1/1,000$)

very rare ($< 1/10,000$)

not known (cannot be estimated from the available data)

Adverse effects depend on the dose and the duration of treatment. Systemic adverse effects are rare but may occur as a result of repeated periarticular injection. As with other intraarticular steroid treatments, transient adrenocortical suppression has been observed during the first week after injection. This effect is enhanced if corticotropin or oral steroids are used concomitantly.

Immune system disorders

Very rare: anaphylaxis-type reactions

Not known exacerbation or masking of infections

Endocrine disorders

Not known menstrual irregularities, amenorrhoea and postmenopausal vaginal bleeding; hirsutism; development of a cushingoid state; secondary adrenocortical and pituitary unresponsiveness, particularly during periods of stress (e.g. trauma, surgery or illness); decreased carbohydrate tolerance; manifestation of latent diabetes mellitus

Psychiatric disorders

Not known insomnia; exacerbation of existing psychiatric symptoms; depression (sometimes severe); euphoria; mood swings; psychotic symptoms

Nervous system disorders

Rare: vertigo

Not known: increased intracranial pressure with papilloedema (pseudotumor cerebri) usually after treatment; headache

Eye disorders

Not known: posterior subcapsular cataracts; increased intraocular pressure; glaucoma

Cardiac disorders

Not known: cardiac failure; arrhythmias

Vascular disorders

Very rare: thromboembolism

Not known: hypertension

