Gastrointestinal disorders

Not known peptic ulcers with possibility of subsequent perforation and haemorrhage; pancreatitis

Skin and subcutaneous tissue disorders

Very rare: hyperpigmentation or hypopigmentation

Not known: impaired wound healing; thin and fragile skin; petechiae and ecchymoses; facial erythema; increased sweating; purpura; striae; acneiform eruptions; hives; rash

Musculoskeletal and connective tissue disorders

Very rare: calcinosis; tendon rupture

Not known: loss of muscle mass; osteoporosis; aseptic necrosis of the heads of the humerus and femur; spontaneous fractures; Charcotlike arthropathy

Renal and urinary disorders

Not known: negative nitrogen balance owing to protein catabolism

General disorders and administration site conditions

Common: Local reactions include sterile abscesses, post-injection erythema, pain, swelling and necrosis at the injection site.

Rare: Excess dosage or too-frequent administration of injections into the same site may cause local subcutaneous atrophy, which, due to the properties of the drug will only return to normal after several months.

Adverse events associated with single intra-articular knee injections of Cingal can be found in the Cingal Investigator's Brochure. These events are expected to be similar for hip injections. In the clinical trial for Cingal in knee OA, adverse events that were related to the injection treatment were:

- injection site pain/swelling
- joint stiffness / swelling / effusion
- arthralgia,
- pain in extremity
- synovitis
- contusion
- subcutaneous nodule
- Baker's cyst

Adverse events not related to the knee for Cingal were:

- headache
- pain in extremity
- upper respiratory tract infection
- back pain

Other risks associated with intra-articular hip injections, regardless of treatment, include:

- temporary injection site pain, swelling or tenderness
- temporary stiffness of the hip
- malfunction of the syringe and/or needle

In rare instances, side effects could include:

- an allergic reaction to the fluoroscopic imaging contrast agent. Symptoms could include redness or inflammation at the injection site or inside the hip joint, hives or itching.
- an allergic reaction to the local anesthetic (lidocaine). Symptoms could include redness or inflammation at the injection site or inside the hip joint, hives or itching.
- injection site infection
- neurovascular, cartilage, or bone damage resulting from the injection itself

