8. SAFETY PROCESSES

Safety of the subjects participating in this clinical investigation will be monitored throughout the clinical investigation using the Adverse Event (AE) reporting process in the EDC system, to identify real and potential safety issues.

Adverse events will be reported according to the ISO 14155:2011, while recognizing and following the requirements including reporting timelines specified in other specific laws, regulations, directives, standards and/or guidelines as appropriate and as required by the countries in which the study is conducted.

All AEs that occur during or after injection will be recorded. Worsening of a condition that existed prior to the study injection should be recorded as an AE. At each assessment during the trial, AEs that have occurred since the previous assessment must be recorded. All subjects will be questioned and evaluated for AEs or complications associated with the procedure. Complications of the injection include, but are not necessarily limited to: pain, swelling, erythema, bleeding and/or infection at the injection site. The Investigator will determine the severity and relationship of each event, as defined above.

AEs observed during the course of this study, regardless of severity or relationship to the device and/or the procedure will be recorded on the CRF. Each reported complication/AE will also include the duration, action taken to address the AE, and the resolution status (e.g. ongoing, resolved). These subjects will continue to be evaluated for safety at all scheduled follow-up points.

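### Section 7.4 ties post-injection AE recording to unexpected symptoms while section 8 requires all AEs; sections 8.2 and 9.2.2 also start AE recording at different points

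*Protocol*

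**What the plan says.** **Which events are recorded.** In Protocol 7.4, the instructions for the period after the injection first ask for an AE evaluation before the subject leaves the clinic. They continue: "All post-treatment signs and symptoms that are unexpected should be recorded as AEs". The subject is then told how the hip should look, "with a request that all unexpected symptoms be reported to a member of the study team". Section 7.4 does not define what counts as unexpected.

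Section 8 applies no such filter. AEs seen during the study "regardless of severity or relationship to the device and/or the procedure will be recorded on the CRF". It adds: "Complications of the injection include, but are not necessarily limited to: pain, swelling, erythema, bleeding and/or infection at the injection site". The AE definition in 8.1 covers any untoward occurrence, including those related to the procedures. The safety endpoint (synopsis and 6.4) is the incidence, severity and relationship of all AEs.

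Local reactions are foreseen elsewhere in the protocol. Section 4.2 lists the related events from the knee trial, beginning with pain and swelling at the injection site, and says of the events known from knee injections: "These events are expected to be similar for hip injections". Section 7.4 itself provides for cold therapy or paracetamol, which "may be prescribed to address short term injection site pain".

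**When recording starts.** Section 8.2 has the investigator document AEs from enrollment onward. Section 9.2.2 says that AEs before the index treatment are not recorded. The synopsis, 6.4, section 8 and the schedule in 7.1 start at the injection or on Day 0.

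**The concern.** The qualifier in 7.4 falls on the events most closely tied to the injection. Local pain and swelling are what an investigator would most naturally call expected, and section 8 names them as complications. A site that works from the visit instructions could leave them out, while a site that works from section 8 would record them. With up to 10 sites, the two rules could be applied side by side.

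At stake is the only safety endpoint of a single-arm trial of 25 subjects, meant to support use in a new joint. Efficacy is not affected.

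The second conflict leaves sites with two incompatible instructions for events between enrollment and the injection.

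**Working it through.** The protocol gives no figure to reproduce. The check is a comparison of its sections, with simple arithmetic for scale.

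**1. Scope, side by side**
- 7.4: the instruction to record, and the request to the subject, both carry the qualifier unexpected.
- Section 8, 8.1 and 6.4: all AEs; no condition on expectedness.
- 4.2 and 7.4: local reactions are foreseen.

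Applied literally, the instruction in 7.4 does not reach reactions that section 8 wants recorded.

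**2. What catches an event that 7.4 misses**
- 7.4 asks for an AE evaluation before discharge, but the sentence on what to record follows directly and narrows it.
- Section 8 has all subjects questioned about AEs, and 7.6 includes AE assessment and a joint examination. The first such visit is Month 1. Taking a 30-day month, that is day 30 ± 3 = 27 to 33 under 7.1, or 30 ± 7 = 23 to 37 under 7.6.
- The diary (7.3.9.6) holds medications, not symptoms. Under 7.3.9.3, the indication for a new medication is recorded as an AE. This catches a reaction only if it was treated, and paracetamol is already the permitted rescue medication (7.3.9.2), so it may not count as new.

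Each route helps. None covers a brief, untreated reaction that the subject was not asked to report.

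**3. Scale**
- Inputs: 25 subjects (synopsis, 6.5). For triamcinolone hexacetonide, 4.2 gives "Common: Local reactions include sterile abscesses, post-injection erythema, pain, swelling and necrosis at the injection site". It introduces its frequency scale with "For assessment of adverse reactions (ADRs) following terms regarding frequency are used", and common there means at least 1/100 and below 1/10.
- Assumption: this range carries over to Cingal in the hip, and subjects are independent.
- Expected subjects with a reaction: 25 × 0.01 = 0.25, up to just under 25 × 0.10 = 2.5.
- Chance of at least one such subject: 1 − 0.99^25 = 22.2%, up to just under 1 − 0.90^25 = 92.8%.
- Effect of one unrecorded subject on the incidence of that reaction: 1/25 = 4 percentage points.

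**4. Start of recording**
- Enrollment is not defined. Section 7.3.1 names it separately from study treatment. The enrollment criteria in 6.6 are checked at both Screening and Baseline.
- If enrollment is at Screening, the disputed window is 7 to 14 days (7.4). With the ±2 days in 7.1 it is 7 − 2 = 5 to 14 + 2 = 16 days.
- If enrollment is at Baseline eligibility, the window is part of Day 0.
- Under either reading, 8.2 and 9.2.2 cannot both be followed within the window.
- A concrete case lies in 7.4 and 6.6.4. The appearance of the aspirate is checked after anesthesia, needle placement and possibly contrast, but before Cingal. A subject excluded at that step may already have reacted to the procedure. Section 8.2 would record the event; 9.2.2 may bar it, since index treatment is not defined.

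**The case against.** The strongest reply is that 7.4 can be read together with section 8 without conflict. A reader might infer that 7.4 limits recording to unexpected symptoms only. It does not say so: it tells sites to record unexpected ones and is silent on the rest, while section 8 and 8.1 state the full rule. That stands. The defect is an instruction that could be followed too narrowly, not a prohibition.

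It can also be said that expected has two senses. In 4.2 the word predicts that the hip profile will resemble the knee profile, and the same text calls those events adverse events. In 7.4 it belongs to advice on how the hip should look. This is fair, and it means 4.2 does not class these reactions as exempt from recording. But 7.4 offers no definition of its own, and foreseen reactions are what a site would most naturally call expected.

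Third, recall at Month 1 is not the only safeguard, because medication taken for a reaction can bring it to light. That also stands, within the limits shown in the working.

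Last, on the start of recording, one clause in 8.2 is out of line with everything else. That is so, which is why it is the lesser point.

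**Conclusion.** The wording conflict is real and should be fixed. Section 7.4 attaches an expectedness condition to AE recording and to subjects' reports that section 8, 8.1 and the safety endpoint do not have. A site following it literally could under-record local reactions. The remaining routes offset this in part.

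The size of any loss cannot be computed from the protocol. A reader might take 22% to 93% as the chance that the endpoint is distorted. It is the chance that at least one reaction occurs, under a frequency class borrowed from one component; how often a site would fail to record it is not known. The 4 percentage points per subject is the firmer figure, and it depends only on 25 subjects being treated.

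A reader might also infer that the conflict over the start of recording biases the safety result. The documents do not support this: the endpoint runs from the injection (synopsis, 6.4) and is analyzed in treated subjects (9.2.3). The conflict concerns what sites enter before that point.

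**What to change.** **Section 7.4.** Replace the qualifier with an instruction to record all AEs as defined in 8.1, whether or not expected, including new or worsened signs and symptoms. Ask subjects to report any new or worsening symptom after the injection. Merely deleting the word unexpected would overshoot. Every subject enters with index-hip walking pain of at least 4 (6.6.3), so unchanged osteoarthritis pain could become an AE in all 25, whereas section 8 counts a pre-existing condition only when it worsens.

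**Sections 8.2 and 9.2.2.** Reconcile them to one defined start of AE recording and apply the same start in the synopsis and 6.4. State how reactions to the procedure before Cingal is injected are recorded, including in subjects then excluded on the appearance of the aspirate. Redefining index treatment as the first procedural step would not be enough by itself. It would depart from the start at injection in 6.4 and leave unclear whether those excluded subjects belong to the Safety Population.

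**Cost.** Changes of wording, with no new visit or procedure. Expect a few more AE entries and possibly a slightly higher reported AE rate.
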